PERFORMANCE Trial

NCT02975505

Document date: 2/13/2025

Statistical Analysis

Safety outcomes, or rates of adverse events, will be tallied using simple proportions and descriptive statistics. Intention-to-treat analysis will be performed. Stratified analyses by diabetes status will be performed given the lack of robust trial data to support intensive BP lowering in patients with diabetes. We will also test for differences in the composite rates of hospitalizations, emergency room visits, and hyperkalemia in the two arms. We will explore differences in the rates of ESKD or cardiovascular events and determine if there is any effect modification of the intervention by level of proteinuria or by diabetes. For patients lost to followup, we plan to use chained multiple imputation to perform analyses.

Sample Size Rationale

We estimate that randomly assigning 90 participants to intensive versus less intensive SBP control would provide 80% power (with 2-sided α of 0.05) to detect a 6-mmHg difference in SBP (with SD of the change in SBP within each arm to be 10 mmHg) between the two arms at month 12. Anticipating approximately a 20% dropout rate given the pill burden and 10% loss to follow-up rate given the traditional known challenges in recruiting and retaining patients with advanced CKD to an interventional trial, we planned to enroll up to 120 participants

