We will permit up to a 30% increase in serum creatinine level after ACEi/ARB initiation or uptitration of dosages of other antihypertensive medications, in accordance with traditional guidelines and published literature (35,36). For patients who experience >30% increase in serum creatinine, the ACEi/ARB dose or other antihypertensive medication will be reduced, with plans for a repeat serum creatinine within 2 weeks. If the serum creatinine continues to be elevated, then the ACEi/ARB will be discontinued. We will also respect the opinion of the patient's nephrologist on this issue. If a nephrologist is concerned about any rise in serum creatinine, we will reduce or discontinue the drug. We will then proceed with the next suggested class of antihypertensive agents to help achieve the target blood pressure.

During the first 8 months of the study, participants will be contacted every other week by study coordinators to note any adverse events including dizziness, falls, syncope, hospitalizations, emergency room visits, acute kidney injury, CV events, or allergic reactions, as well as adherence to medication regimen and medication side effects such as diuresis, impotence, cough, lack of energy and sleepiness, lightheadedness on standing, or headaches.

Laboratory Tests

Basic metabolic panel and urine chemistry laboratory tests are obtained at baseline and at months 1, 2, 4, 8, 12, and every six months thereafter but timed as closely to clinical laboratory tests as possible (to avoid additional burden on participants) in a pragmatic approach. Labs are closely monitored by study investigators and medications titrated

accordingly to ensure the safety of all participants. Additional laboratory testing is performed as needed.

Follow-Up Timeline

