The timeline of study visits during the one-year of follow-up is outlined in Figure 1. Participants are instructed to take weekly home BP readings for the first 4 months of the study, or until target SBP levels are achieved for two consecutive weeks. Once participants reach target SBP levels, home BP readings can be taken on a monthly basis over a one-week period each month. If participants maintain their target SBP levels after 8 months, home BP readings can be taken every two months thereafter. Participants will maintain their respective SBP target levels for the remainder of the study after month 8. If mean weekly SBP readings are > 4 mmHg outside the target range, antihypertensive therapy titration is resumed weekly until target SBP levels are achieved again for two consecutive weeks.

Participants are seen in person at Months 2, 4, 8, and 12, and every 6 months thereafter, but visits will be timed as close to their clinical visits as possible to avoid additional burden on participants in a pragmatic approach. In-person follow-up visits consist of a brief physical exam, office BP readings which will be obtained and used to calibrate the QardioArm® device to ensure accuracy of its readings, and laboratory testing. Patients will be contacted throughout the study via phone or secure text messages depending on patient preference. Adherence to antihypertensive therapy treatment will be assessed by administering a questionnaire during every in-person visit and follow-up phone call to ask participants if they are taking antihypertensive medications as prescribed and if they missed any doses since last follow-up. Adverse events (including emergency room visits or hospitalizations) and onset of ESKD, defined as initiation of chronic dialysis or receipt of kidney transplant, are also ascertained during follow-up. Participants will be followed indefinitely unless they choose to disenroll from the study or are lost to follow-up.

Outcomes measures

The primary outcome will be feasibility of achieving at least a 6 mmHg separation between intensive BP control and usual BP control arms at month 8. A secondary outcome will be the difference in BP between the two treatment strategies at study closeout. Adherence to home BP monitoring will be measured by the number of weeks participants successfully complete the minimum number of home readings.

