Safety of our intervention will also be a secondary outcome and will be determined by a composite of adverse events including hyperkalemia ($K \ge 6.0 \text{ meq/L}$), self-reported falls, syncope, or acute kidney injury (AKI) requiring emergency room visit or hospitalizations. Discharge summaries from emergency room visits and hospitalizations in patient health records will be reviewed and events adjudicated by two study investigators. In addition, onset of ESKD will not be a censoring event; patients will be encouraged to continue to check home BPs following transplant or dialysis, but no study-driven active titration of antihypertensive agents will occur after ESKD onset.

Statistical analysis

Safety outcomes, or rates of adverse events, will be tallied using simple proportions and descriptive statistics. Intention-to-treat analysis will be performed. Stratified analyses by diabetes status will be performed given the lack of robust trial data to support intensive BP lowering in patients with diabetes. We will also test for differences in the composite rates of hospitalizations, emergency room visits, and hyperkalemia in the two arms. We will explore differences in the rates of ESKD or cardiovascular events and determine if there is any effect modification of the intervention by level of proteinuria or by diabetes. For patients lost to follow-up, we plan to use chained multiple imputation to perform analyses.

Sample size rationale

Randomizing 96 participants to strict vs usual BP control will provide 80% power (with 2-sided α of 0.05) to detect a 6-mmHg difference in SBP (with SD difference of 10 mmHg) between the two arms at month 8. Anticipating approximately 25% dropout, we plan to enroll 120 participants. An effect size of similar magnitude has been reported previously in telemonitoring feedback from pharmacists in adult home BP monitoring trials (37).

List of Abbreviations

BP- blood pressure

CKD- chronic kidney disease

CV- cardiovascular

SBP- systolic blood pressure

ESKD- end-stage kidney disease

SPRINT- Systolic Blood Pressure Intervention Trial

eGFR- estimated glomerular filtration rate

MDRD- Modification of Diet in Renal Disease

RAAS- renin-angiotensin-aldosterone system

AKI- acute kidney injury

BMP- basic metabolic panel

UPCR- urine protein creatinine ratio

ABPM- ambulatory blood pressure monitoring

DBP- diastolic blood pressure

MAP- mean arterial pressure

ARB- angiotensin receptor blockers

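### The declared safety composite is only tallied, while the one committed between-arm safety test uses a different list of events

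*SAP*

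**What the plan says.** **The declared outcome.** Protocol, Outcomes measures: "Safety of our intervention will also be a secondary outcome and will be determined by a composite of adverse events including hyperkalemia" (potassium of at least 6.0 meq/L). The list continues with "self-reported falls, syncope, or acute kidney injury (AKI) requiring emergency room visit or hospitalizations". On how events are confirmed: "Discharge summaries from emergency room visits and hospitalizations in patient health records will be reviewed and events adjudicated by two study investigators".

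**The analysis.** The Protocol (Statistical analysis) and the SAP (Statistical Analysis) use the same sentences. First: "Safety outcomes, or rates of adverse events, will be tallied using simple proportions and descriptive statistics". Then: "We will also test for differences in the composite rates of hospitalizations, emergency room visits, and hyperkalemia in the two arms". Differences in ESKD and cardiovascular events are only to be explored. Neither document names a between-arm effect measure or confidence interval for either composite.

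**What is recorded.** Under Antihypertensive Therapy Titration Intervention, the coordinators are to "note any adverse events including dizziness, falls, syncope, hospitalizations, emergency room visits, acute kidney injury, CV events, or allergic reactions". The Follow-Up Timeline section has "Adverse events (including emergency room visits or hospitalizations) and onset of ESKD" ascertained during follow-up.

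**The concern.** The Protocol describes the pilot as a study of safety and feasibility (Study design), and it justifies the initial 2:1 allocation by the need for safety data on the intervention (Randomization). The plan also goes beyond description: it commits to a formal between-arm comparison of adverse events. But that comparison is attached to a composite that shares only hyperkalemia, by name, with the declared one. Falls, syncope and AKI drop out as named components, and hospitalizations and emergency visits come in with no stated restriction by cause.

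At stake is what the one planned safety comparison means. A difference, or its absence, in the tested composite need not carry over to the declared outcome, and for the declared outcome the plan promises only a tally.

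**Working it through.** **1. The plan's own figures.** The documents give no event rate, margin, power or precision for either composite. The sample sizes (96 in the Protocol, 90 in the SAP) concern systolic pressure only, so there is no figure to reproduce on this point.

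**2. The two lists side by side.**

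| Component | Declared composite | Tested composite |
|---|---|---|
| Hyperkalemia | yes, at least 6.0 meq/L | yes, threshold not repeated |
| Self-reported falls | yes | not named |
| Syncope | yes | not named |
| AKI requiring a visit or admission | yes | not named; enters through the visit |
| Hospitalization or emergency visit as such | not named | yes, no cause stated |

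**3. The visit requirement has two readings.**

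- *It qualifies AKI only*, as the words on self-report suggest. Falls and syncope without a visit then belong to the declared outcome but to no named comparison.
- *It qualifies falls, syncope and AKI*, as adjudication from discharge summaries suggests. The tested composite then contains every listed event, but may add visits for unrelated causes.

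On either reading, the lists as written are not the same.

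**4. Can size or direction be derived?** Only by assumption. Let p be the proportion of patients with a declared event, u the share of those whom the tested composite misses (same in both arms), and b the proportion with other visits, independent of declared events. The tested proportion is 1 − (1 − b)(1 − p(1 − u)). All rates below are assumed; intervention is given first.

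| Assumption | Declared | Tested | Tested difference |
|---|---|---|---|
| u = 0, b = 10% in both arms | 40% vs 20% | 46% vs 28% | 18 points |
| u = 0, b = 50% in both arms | 40% vs 20% | 70% vs 60% | 10 points |
| u = 25%, b = 0 | 40% vs 20% | 30% vs 15% | 15 points |
| u = 50%, b = 0 | 40% vs 20% | 20% vs 10% | 10 points |
| u = 0, b = 20% vs 10% | 40% vs 20% | 52% vs 28% | 24 points |
| u = 25%, b = 20% vs 10% | 40% vs 20% | 44% vs 23.5% | 20.5 points |
| u = 0, b = 20% vs 10% | 20% vs 20% | 36% vs 28% | 8 points |

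Against a declared difference of 20 points, the tested difference may be smaller, larger or almost the same. It may also be present when the declared composite does not differ. No direction follows.

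**5. Precision of an estimate on the declared composite.** Allocation: 75 at 2:1 gives 50:25, and the remaining 45 at 1:1 give 22.5:22.5, in total 72.5:47.5. The Wald 95% half-width is 1.96 × √[p₁(1 − p₁)/n₁ + p₂(1 − p₂)/n₂].

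- 40% vs 20%: 1.96 × √(0.24/72.5 + 0.16/47.5) = 1.96 × 0.0817 = 0.160, so 20 points (4 to 36).
- 20% vs 10%: 1.96 × √(0.16/72.5 + 0.09/47.5) = 1.96 × 0.0640 = 0.126, so 10 points (−3 to 23).

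With the Protocol's 25% dropout, 120 × 0.75 = 90 remain, about 54:36. The half-widths become 1.96 × √(0.24/54 + 0.16/36) = 0.185 and 1.96 × √(0.16/54 + 0.09/36) = 0.145.

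**The case against.** The strongest reply has four parts.

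*The documents already rank the two composites.* Only the first is declared an outcome, and the test is introduced as something done in addition. This stands. A reader might infer that the plan leaves open which composite carries the safety conclusion, but the Outcomes measures text says safety is determined by the declared one. What is missing is a label on the tested composite and a comparison on the declared one.

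*A descriptive safety analysis is normal in a pilot.* This also stands. The tally may well be reported by arm, and a reader could then compute a crude difference. The lack of a named effect measure would not by itself be a point worth raising. It becomes one because the plan does commit to a between-arm safety test and places it elsewhere.

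*The lists may be closer than they look.* The declared list is open (it says *including*), visits and hospitalizations are recorded as adverse events, and the test sentence may be loose shorthand for much the same events. This is possible, and the lack of a cause restriction is read from silence. But the adverse-event list names visits beside falls, syncope and AKI as separate entries, which speaks against shorthand. An open list is itself a reason to state membership.

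*The illustration proves little.* Agreed. Every rate is assumed, and the plan's composite rates may mean events over follow-up time rather than one yes/no result per patient.

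**Conclusion.** The mismatch is real and can be seen in the text: the declared safety outcome gets a tally, and the only committed between-arm safety test uses a different list of events.

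A reader might go further and infer that the tested composite will dilute or hide a harm. The documents do not support that. They give no event rates, and the assumed scenarios move the tested difference both down and up.

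The one size that bears on the remedy is precision: a 95% CI half-width of about 13 to 16 points for the declared composite. It rests on assumed rates of 20% vs 10% and 40% vs 20%, one yes/no result per patient, and all 120 randomized patients contributing. An estimate would be imprecise but would say plainly what the pilot can and cannot exclude.

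This is a minor improvement to a secondary outcome. The primary outcome is unaffected.

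**What to change.** In both documents:

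1. Make the between-arm safety comparison on the declared composite: the risk difference with 95% CI for patients with at least one event by a fixed time point, for example month 12, with each component shown by arm. A fixed time point is needed because follow-up is otherwise indefinite.
2. Close the open list of components, and state whether the visit requirement covers AKI alone or falls and syncope as well.
3. Label the test of hospitalizations, emergency visits and hyperkalemia as supporting, and state whether visits for any cause count.

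The cost is a few sentences in each document and one more estimate from data already collected. There are three downsides. The intervals will be wide. Self-reported falls are open to reporting bias in a non-blinded trial, which is a reason to keep the visit-based test alongside. Capture of falls without a visit may also be less complete later on, since the frequent contacts are stated only for the early period: "During the first 8 months of the study, participants will be contacted every other week by study coordinators". The choice of time point should take this into account.

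### The committed test of hospitalizations, emergency visits and hyperkalemia has only simple proportions behind it, which ignore repeat events and unequal follow-up; it needs a person-level rate model.

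*SAP*

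**What the plan says.** The Protocol (Statistical analysis) and the SAP (Statistical Analysis) carry the same commitment, to "test for differences in the composite rates of hospitalizations, emergency room visits, and hyperkalemia in the two arms". Neither states the test, the unit (events or participants), the handling of repeat or linked events, the time window or the use of person-time.

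The one method given for safety data is: "Safety outcomes, or rates of adverse events, will be tallied using simple proportions and descriptive statistics". That sentence treats rates and proportions as the same thing. It describes tallying and does not specify the test.

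Three other parts of the Protocol bear on this:

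- **Randomization:** allocation is 2:1 for the first 75 participants and 1:1 afterwards.
- **Follow-Up Timeline:** follow-up has no fixed end unless a participant leaves or is lost.
- **Outcomes measures:** the secondary safety outcome is a different composite, namely hyperkalemia with "self-reported falls, syncope, or acute kidney injury (AKI) requiring emergency room visit or hospitalizations".

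**The concern.** The three components can recur in one person, and they overlap: an emergency visit may become an admission, and hyperkalemia may lead to both. A participant followed for three years also has more chance of at least one event than one followed for one year. A simple proportion handles neither feature.

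The unequal follow-up does not balance between arms. Early participants were allocated 2:1 and later ones 1:1, so the intensive arm has the larger share of long follow-up. A proportion taken at closeout would then differ between arms even if the true rates were equal, and the intensive arm would look worse.

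The Protocol (Study design) gives safety and feasibility as the purpose of the trial. This is the only between-arm safety comparison that the plan commits to test; ESKD and cardiovascular events are to be explored. The trial is also unblinded, so the method should be fixed in advance.

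**Working it through.** **The plan's own figure.** The only sample size calculation concerns SBP. The SAP plans "randomly assigning 90 participants to intensive versus less intensive SBP control" for a 6-mmHg difference, "with SD of the change in SBP within each arm to be 10 mmHg". The normal formula gives 2 × (1.96 + 0.8416)² × 10² / 6² = 43.6, so 44 per arm (88 in total). The t-test version gives 44.6, so 45 per arm (90 in total). The SAP's 90 is reproduced, but it says nothing about the composite, for which no event rate, effect or power is stated.

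**Inputs from the documents.** Enrolment of 120. The first 75 at 2:1 give 50 and 25; the other 45 at 1:1 give 22.5 each. The arms are about 72.5 and 47.5, taken as 72 and 48, so early participants make up 50/72 = 69% of the intensive arm and 25/48 = 52% of usual care.

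**Assumed, not in the documents.** Rate λ of 0.3 to 1.0 events per person-year; gamma frailty with variance k; at closeout, 3 years of follow-up for the first 75 participants and 1 year for the rest.

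**Step 1: proportions at closeout, equal true rates.** The chance of any event in t years is 1 − (1 + kλt)^(−1/k), or 1 − exp(−λt) when k = 0. Take λ = 0.5 and k = 1, which gives 0.600 at 3 years and 0.333 at 1 year.

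- Intensive: (50 × 0.600 + 22 × 0.333)/72 = 0.519
- Usual care: (25 × 0.600 + 23 × 0.333)/48 = 0.472
- Spurious difference: 0.046
- Standard error used by the test: √[0.5 × 0.5 × (1/72 + 1/48)] = 0.0932
- True standard deviation of the difference, given the follow-up mix: 0.0899
- Rejection toward harm: Φ[(0.0463 − 1.96 × 0.0932)/0.0899] = 6.5%
- Rejection toward benefit: Φ[(−0.0463 − 1.96 × 0.0932)/0.0899] = 0.5%
- Total: 7.0%, where each tail should be 2.5%

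The same calculation gives 6.2% at λ = 0.5, k = 2 and 10.8% at λ = 1.0, k = 0. Simulation gives about 5.5% to 11% over most of the grid, and 13% in the corner with 1.0 events per year and no frailty. At frailty variance 1 the error is about 7% throughout, so the upper end requires little heterogeneity between people.

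**Step 2: power over a fixed year, rate ratio 1.75, k = 1.** Over a fixed year the proportion test keeps its level (simulated 0.048 to 0.054). At λ = 0.5 the proportions are 0.333 and 0.467.

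- Proportion test: Φ[(0.1333 − 1.96 × 0.0918)/0.0899] = 30%
- Negative binomial: the SE of the log rate ratio is √[(1/0.5 + 1)/48 + (1/0.875 + 1)/72] = 0.304, and Φ(0.560/0.304 − 1.96) = 45%

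| λ per year | Any-event proportion | Negative binomial |
|---|---|---|
| 0.3 | 26% | 34% |
| 0.5 | 30% | 45% |
| 1.0 | 32% | 60% |

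Simulation gives 25% to 33% for the proportion test against 33% to 62% for robust-variance Poisson, whose own type I error is 5% to 7%.

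**Step 3: if raw events were pooled as independent.** The variance is inflated by V = 1 + kλ over one year, and the true size is 2[1 − Φ(1.96/√V)]. At k = 1 this is 8.6%, 12.1% and 16.6% for λ = 0.3, 0.6 and 1.0. Simulated Wald tests give 8.0%, 11.5% and 16.3%. Exact tests run a little lower, so about 7% to 15% is a fair summary. At k = 0 there is no inflation.

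If half of all episodes were also counted twice, V = (2.5λ + 2.25kλ²)/(1.5λ). The size is then 13% at k = 0, and 21% and 27% at k = 1 for λ = 0.5 and 1.0.

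**The case against.** The strongest reply is that the plan is silent rather than wrong. A count model with robust variance is compatible with testing composite rates, and nothing says that events would be pooled as independent. A reader might infer that the test must be either badly anti-conservative or badly underpowered, with false-positive rates of 21% to 41%. The documents do not support that. Those rates need pooled events, assumed frailty and an assumed half of episodes counted twice, partly over several years. With neither frailty nor double counting, the error is about 4% to 5%. The wording on proportions leans toward counting participants.

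Other parts of the reply also carry weight:

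- Any event and event rate are both legitimate questions, and over a fixed window the proportion test is valid.
- The power loss is modest at low rates (26% versus 34% at 0.3 per year), and at 0.3 to 0.5 per year the count model also misses the excess more often than not.
- Safety is a secondary outcome in a pilot whose primary outcome is SBP separation.
- Two investigators already review discharge summaries and adjudicate events, although that is not a rule for merging linked events.

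The Protocol also plans a sensitivity analysis for interaction between intervention and allocation phase. That asks whether the effect differs by phase. It does not correct an unadjusted comparison for unequal follow-up.

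These replies limit the size of the concern. They leave standing that the only named method ignores person-time in a trial whose design makes person-time unequal between arms.

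**Conclusion.** The concern holds in a bounded form. The plan commits to a test of rates and names only a method for proportions. If that method is applied at closeout, it tilts toward apparent harm in the intensive arm: type I error is about 5.5% to 11%, assuming 3 versus 1 years of follow-up by phase. Over a fixed year the tilt disappears, but a rate ratio of 1.75 is detected with 25% to 33% power instead of 33% to 62%, assuming frailty variance 1 and 0.3 to 1.0 events per person-year. Inflation from pooling raw events is a risk that the text leaves open, not something it prescribes. The documents give no event rate, dispersion, overlap or follow-up distribution, so all these sizes are conditional. The matter is moderate: it should be settled before analysis, but it does not touch the primary outcome.

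**What to change.** State in the SAP that:

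1. The composite is analysed with one row per participant over a stated window. The choice should take account of the fact that every-other-week adverse event contact is described only for the first 8 months.
2. An emergency visit and the admission and hyperkalemia belonging to it count as one episode, under a date-based rule fixed in advance and applied without reference to arm.
3. Arms are compared by negative binomial or robust-variance Poisson regression, with log follow-up time as offset, adjusted for allocation phase and diabetes stratum.
4. The rate ratio is reported with its 95% CI, and the proportion with any event is given as a descriptive companion.
5. The offset is reconciled with the planned multiple imputation, so that follow-up after loss is not both imputed and excluded.
6. The relation of this composite to the one in the Protocol's Outcomes measures is made explicit.

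The cost is SAP wording and some programming. It needs event dates, which the documents do not explicitly say are recorded, although discharge summaries are already reviewed. The downsides are that the merging rule must be applied to every episode, and that linking a potassium value to an admission leaves room for judgement in an unblinded trial, which is why the rule should rest on dates. Power stays limited under any method.

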If patients meet all inclusions and exclusion criteria, we will check with their nephrology providers prior to approaching participants to ensure their candidacy in our study.

Baseline Visit

During the baseline visit, participant eligibility is confirmed, written consent is obtained, and demographic, co-morbidity, and laboratory data are collected. A brief physical examination is performed and three automated office BP readings in the seated position followed by two standing BP readings are recorded one minute apart after five minutes of quiet rest. At the baseline visit, enrollees are provided with a QardioArm® device and trained to use the device to take standardized home BP measurements.

Participants are asked to take home BPs for a one-week baseline period to ensure continued eligibility and compliance with our protocol prior to randomization, with a minimum of 6 readings required over the one-week period. Participants are also asked to complete 24-hour ambulatory blood pressure monitoring (ABPM) during their baseline period. Patients who refuse to undergo 24-hour ABPM are not excluded from study.

Randomization

Eligible patients who complete the one week of baseline home readings will be randomized to either a home SBP target of <120 mmHg (intervention group) or 130-140 mmHg (usual care group) in 2:1 ratio until 75 participants are enrolled, and participants will be subsequently randomized in 1:1 ratio thereafter. The rationale for the 2:1 ratio for the first 75 patients is to ensure that we initially capture enough safety data on participants randomized to intervention, but we plan to transition to 1:1 ratio randomization thereafter. We will conduct a sensitivity analysis comparing the effect during the 2:1 randomization phase of the trial and 1:1 phase to determine if there is an interaction between the intervention and the phase of the trial.

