Once patients are screened and deemed eligible, study personnel will notify nephrologists of their patients' eligibility and obtain assent for patient participation in the trial prior to randomization. Stratified permuted-block randomization will be performed with stratification by diabetes status in order to ensure that patients with diabetes who have previously been excluded from many trials of intensive BP lowering (8–10) are represented in our pilot study. Investigators will be blinded to the ordering of the randomization blocks and their respective sizes. The generation of allocation sequence is performed by and only accessible to the study coordinator for assignment of participants to the intervention and not accessible to investigators. Patients are contacted via phone or secure messaging to begin active titration of their antihypertensive regimens to achieve their assigned target SBPs after randomization.

Home blood pressure monitor

QardioArm[®] is a wireless Bluetooth-enabled home BP monitor that is validated by the European Society of Hypertension Protocol and the American Heart Association (31) and has a strong direct linear correlation (r=.96) with the previously validated and widely accepted Omron M3[®] BP device (32). The device is compatible with most smartphones and allows for real-time

wireless transmission of BP readings through an online phone application. The device is also accompanied by a secure platform used by providers for BP data transmission, monitoring, download, and storage. All participants are provided a device at no cost, and Bluetooth linkage between the device and smartphone are setup by study personnel at the baseline visit.

Office BP readings during study visits

Office BPs are measured at the baseline, 2, 4, 8, and 12-month study visits (Figure 1), and every six months thereafter. Participants are seated quietly in a room with the study coordinator for 5 minutes before BPs are taken. Three measurements are taken one minute apart. Participants are then be asked to stand for two minutes and two standing BPs are recorded one minute apart. One study coordinator will be present during all office BP measurements.

Intervention

Blood Pressure Targets

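### The primary SBP comparison has no stated analysis; a month-8 model adjusted for baseline SBP, diabetes stratum and randomisation phase would add precision at the cost of wording

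*SAP*

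**What the plan says.** The protocol's Outcomes measures section defines the primary outcome as the feasibility of reaching a separation of at least 6 mmHg between arms at month 8. It does not say whether this is home or office pressure.

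The statistical analysis text is essentially the same in both documents. It covers safety proportions, intention-to-treat, analyses by diabetes status, composite event rates, ESKD and cardiovascular events, effect modification and multiple imputation. It gives no analysis of SBP.

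The sample-size sections are the only indirect guide:

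- SAP, Sample Size Rationale: "randomly assigning 90 participants to intensive versus less intensive SBP control" is said to give 80% power for 6 mmHg at month 12, "with SD of the change in SBP within each arm to be 10 mmHg".
- Protocol, Sample size rationale: 96 participants are said to give 80% power "to detect a 6-mmHg difference in SBP (with SD difference of 10 mmHg) between the two arms at month 8".

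Three relevant variables are available. On baseline pressure, the Baseline Visit section says "Participants are asked to take home BPs for a one-week baseline period", before randomisation. On the stratum, the Randomization section says "Stratified permuted-block randomization will be performed with stratification by diabetes status". The same section sets 2:1 allocation for the first 75 patients and 1:1 afterwards, with a sensitivity analysis for interaction between treatment and phase.

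**The concern.** With no stated analysis, a reader must infer one from the sample size, and the two documents point in different directions. The SAP's SD belongs to a change score. The protocol's wording could describe a plain comparison of month-8 values, or something else. These analyses have different variances, and neither is the most precise one available from data already collected.

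Two things are at stake. The first is precision: a change-score analysis has no margin at the planned size, while baseline adjustment gives some. The second is choice after the fact: the trial is not blinded, and leaving change score, raw value or adjusted value open allows the selection to follow the results.

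Phase matters separately. Because the allocation ratio changes after patient 75, the arms differ in their mix of early and late enrolees. If SBP drifts over enrolment, a pooled comparison that ignores phase would be biased.

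**Working it through.** **Inputs from the documents.** Difference 6 mmHg; two-sided α 0.05; SD of change 10 mmHg within each arm (SAP); N = 90 (SAP) or 96 (protocol); 120 enrolled, 2:1 for the first 75 and then 1:1.

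**Assumptions not in the documents.** A baseline to follow-up correlation ρ of 0.3 to 0.8; equal baseline and follow-up variances; and the SAP's month-12 SD of 10 applied at month 8.

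**Step 1: reproduce the SAP's figure.** For a 1:1 two-sample comparison with SD 10, the normal formula gives 44 per arm (88 in total). The t-based version gives 45 per arm (90), with power 80.4%. The SAP's N = 90 is therefore a change-score calculation at equal allocation. Ninety-six at 1:1 gives 82.9%.

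**Step 2: planned allocation.** The intervention share is (50 + 22.5)/120 = 60.4%, so 90 evaluable patients split as 54.4 and 35.6. The SE is 10 × √(1/54.4 + 1/35.6) = 2.16 mmHg and the noncentrality is 6/2.16 = 2.78. Noncentral t power on 88 df is **78.6%**.

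**Step 3: the other two analyses.** With the SD of change held at 10:

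- raw follow-up SD = 10/√(2(1 − ρ));
- baseline-adjusted residual SD = 10 × √((1 + ρ)/2).

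Power with 90 evaluable and the planned allocation:

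| ρ (assumed) | Raw SD | Raw month-8 | Adjusted SD | Baseline-adjusted | Change score |
|---|---|---|---|---|---|
| 0.3 | 8.45 | 90.3% | 8.06 | 92.7% | 78.6% |
| 0.4 | 9.13 | 85.4% | 8.37 | 90.8% | 78.6% |
| 0.5 | 10.00 | 78.6% | 8.66 | 88.9% | 78.6% |
| 0.6 | 11.18 | 69.2% | 8.94 | 86.8% | 78.6% |
| 0.7 | 12.91 | 56.9% | 9.22 | 84.8% | 78.6% |
| 0.8 | 15.81 | 41.4% | 9.49 | 82.7% | 78.6% |

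**Step 4: heavier loss.** If the SAP's 20% and 10% losses add, 120 × 0.70 = 84 remain. The change score then gives 75.7%, and baseline adjustment 86.6% (ρ = 0.5), 82.2% (0.7) and 80.0% (0.8).

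**Step 5: price of adjusting for phase.** Arm and phase are correlated, so some information is spent. Within phases it is 50 × 25/75 + 22.5 × 22.5/45 = 16.67 + 11.25 = 27.92, against 72.5 × 47.5/120 = 28.70 pooled. The ratio is 0.973, which widens the SE by a factor of 1/√0.973 = 1.014. That takes about one percentage point off the adjusted powers above, which allow for baseline only.

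**The case against.** **Equal variances are assumed.** In general the SD of change equals the follow-up SD when ρ = SD(baseline)/(2 × SD(follow-up)), which is 0.5 only if the two SDs match. With illustrative SDs of 15 at baseline and 10 at month 8 and ρ = 0.75, the variance of change is 225 + 100 − 225 = 100. A raw comparison then loses nothing against the change score. Both arms are titrated to a target, which could well narrow month-8 SBP. This stands, and it limits the raw-comparison column. It does not touch the case for adjustment: change score and raw value fix the baseline slope at 1 and 0, while the model estimates it, so the residual SD is no larger than either. In this example it is 10 × √(1 − 0.5625) = 6.6.

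**A reader might infer that a month-8 comparison lacks the assumed SD.** The documents do not support that. The protocol's "with SD difference of 10 mmHg" is undefined; if it means the month-8 SD, a raw comparison has it by definition. At correlations below 0.5, under equal variances, the raw comparison beats the change score.

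**A reader might infer that ignoring the diabetes stratum inflates the standard error.** It would, to the extent that diabetes predicts SBP, but the documents give nothing from which to size this. The planned analyses by diabetes status are justified by the lack of evidence in diabetes, so they read as subgroup analyses rather than adjustment.

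**This is a pilot with a feasibility outcome.** The documents do not say whether success is an observed separation or a significant one, and a model does not settle that. An adjusted difference with its interval serves either reading.

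**The analysis might adjust anyway.** It might; the documents are silent rather than opposed. That is a reason to write it down.

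**Conclusion.** The point holds as a gap in the analysis plan and a missed gain in precision. No analysis of the primary SBP separation is stated, and no use of baseline SBP, stratum or phase in the main comparison is described.

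It does not show that the sample size is wrong. N = 90 reproduces on the SAP's own inputs, and the change-score test at the actual allocation has 78.6% power, close to plan.

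Given an SD of change of 10 at month 8, 90 evaluable patients and equal variances, baseline adjustment gives 92.7% to 82.7% over ρ of 0.3 to 0.8, less about one point for phase. The gain over the change score is present throughout that range. The shortfall of a raw comparison is conditional, appearing only from ρ of about 0.5 upwards and reaching 41.4% at 0.8. The documents give neither the correlation nor the variances. The gain from the stratum cannot be quantified, and the case for phase rests on protection against drift, not on precision.

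**What to change.** - **Primary analysis.** Prespecify a linear model of month-8 SBP on arm, baseline SBP measured the same way, diabetes stratum and randomisation phase. Report the adjusted difference with its 95% CI.
- **Measurement.** State whether the SBP is home or office. Office pressure is also taken at baseline and month 8, so either is workable, but home SBP is the titration target and is collected for a week before randomisation.
- **The SD.** The sponsor should state which SD the 10 mmHg is, in both documents. The protocol's figure should not simply be relabelled as an SD of change, because the text does not establish that.
- **Reconcile.** Month 8 with month 12, and 96 with 90 participants.

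The cost is wording: every covariate is already recorded. It is a free improvement provided it is fixed before the outcome data are analysed. The documents do not show whether that point has passed; if it has, the model should be reported as specified late.
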